10.2 OUTLINE OF STUDY PROCEDURES AND ASSESSMENTS

The first visit for this extension study is combined with the Month 6 visit of the main study. Therefore, the Month 6 assessments from the main study will not have to be duplicated at the start of the extension study. The study visit schedule is depicted in Figure 2 and the schedule of assessments is detailed in Appendix A and Appendix B.

* At the end of the 6-month follow-up, subjects with a BMD decrease from baseline of > 1.5% for lumbar spine and/or > 2.5% for total hip compared to main study baseline will have an additional DXA scan 6 months later.

Figure 2 : Schedule of Visits

All visits should take place at the end of the defined period (i.e. Month 7 visit should be scheduled at the end of Month 7, Month 8 visit should be scheduled at the end of Month 8, etc.). One month is defined as 28 days/4 weeks. All visit dates are calculated from the date the patient started treatment in the main study (Day 1 visit of 18-OBE2109-003 Edelweiss 3):

- Month 7 (Day 197), Month 8 (Day 225), Month 9 (Day 253), Month 10 (Day 281), Month 11 (Day 309) and Month 12 (Day 337) for the Treatment Period,
- Month 1 Extension FU (Day 365), Month 3 Extension FU (Day 421) and Month 6 Extension FU (Day 505) for the Follow-up Period.

A window of -3/+2 days is allowed for Month 7 visit, and of ± 3 days for each of the following visits during the Treatment Period. A window of ± 7 days/1 week is allowed for each visit scheduled during the Follow-Up Period.

The timing of events is shown in the Schedule of Assessments (Appendix A and Appendix B).

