10.2.2 Post-treatment Follow-Up Period

Up to Month 6 Extension FU visit, the subject will continue to record on her eDiary, daily at approximately the same time each evening, her use of provided/prescribed analgesics, uterine bleeding, pelvic pain, dyspareunia, dyschezia and daily function.

The subject will be asked to bring her eDiary at each visit to the site during the entire Follow-Up Period.

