5.2. Data Conventions

5.2.1. Last extension treatment administration date, End of extension Study date and Period definitions

The last extension treatment administration date will be defined as the date from the treatment termination reported in the extension period eCRF page. If this date is missing, the last date with a drug intake in the eDiary that is inferior or equal to Month 12 visit or the last available date with a drug intake in the eDiary if the subject discontinued the extension treatment will be used.

For subjects who entered the extension, the end of the extension study date will be the last assessment date in the extension study defined as last assessment recorded in the eCRF (excluding end date of adverse events and concomitant medications) or ediary date (excluding drug intakes recorded after last extension treatment administration date). This will not necessarily be the same date as last assessment date as recorded in the eCRF.

For each 28-day period prior to Month X (except Month 12), the end of the period will be defined as the Month X visit date. If subject discontinued prior to Month X, the end of the period will be the date from the treatment termination of extension period eCRF page or the last date with a drug intake in the eDiary if missing. If the subject missed the Month X visit (but did not discontinue), the subject might still have filled the diary during that time: the theoretical Month X date will be used to define the end of the 28-day period. The theoretical Month X is defined with respect to Day 1 as Month X= Day 1+ $28^{*}X$.

For the 28-day period prior to Month 12, the end of the period will be defined as the last extension treatment administration date.

Note:

For Adverse Events, Concomitant Medications and Daily diaries data collected on the Month 6 date will be part of the extension for subjects entering the extension study.

For Adverse Events, Concomitant Medications and Daily diaries, data collected on the Month 12 date will be part of the Extension Follow-up period for subjects entering the Extension follow-up period.

The extension treatment period will be defined as Month 6 up to (Month 12 date -1) or treatment discontinuation date.

The extension follow-up period will be defined as the Month 12 date or (treatment discontinuation date+1) up to the extension follow-up end date (for subjects who entered the extension follow-up).

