6.6.8.5. Time to the first post-treatment menses

The first post-treatment menses will be defined from the Vaginal Bleeding daily ediary, as the first day for which the subject recorded bleeding after the last treatment administration date of the extension study, i.e., the first day with "BLEEDING" or "HEAVY BLEEDING" after the last treatment administration date of the extension study.

Time to first post-treatment menses is defined as:

Time to first post-treatment menses (days) = (day of first post-treatment menses – last treatment administration date in extension) + 1

Only data from the follow-up extension period will be included, and the analysis will be provided on the Follow-up Extension Safety Analysis Set, by treatment group.

Subjects who have not recorded any bleeding up to the end of the follow-up extension period will be considered as right-censored data at the last ediary vaginal bleeding record date before the end of the extension follow-up period (as defined in section 5.2) with time of censoring = last non-missing ediary vaginal bleeding record date – last treatment administration date in extension +1.

The probability of subjects having bleeding will be displayed by treatment group in the form of cumulative probability curves estimated using the non-parametric Kaplan-Meier method. Point estimates and corresponding 2-sided 95% CIs using the Greenwood's variance estimate will be provided at 28 days, 56 days, 84 days, 112 days, 140 days, 168 days, 196 days after the last treatment administration date in extension. Percentiles (25th, 50th, and 75th) and corresponding 2-sided 95% CIs will also be provided; "N/A" will be presented for any of the percentiles not reached.

Subjects with or without first post-treatment menses, time to first post-treatment menses, end of study status and end of study date will be presented in a by-subject listing.

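### The 196-day estimate of return of menses lies beyond diary follow-up on protocol dates, and restricting the data to the follow-up period can drop bleeding when a completer's last dose is early (minor)

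*SAP*

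**What the plan says.** Time to first post-treatment menses is a listed safety endpoint (Protocol 7.2, SAP 3.3). SAP 6.6.8.5 takes the event from the daily vaginal-bleeding diary, as the first day of bleeding or heavy bleeding after the last extension dose. Its clock is "day of first post-treatment menses – last treatment administration date in extension) + 1". Women without a bleed are treated as "right-censored data at the last ediary vaginal bleeding record date before the end of the extension follow-up period".

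Kaplan-Meier estimates with Greenwood 95% intervals are to be tabulated every 28 days, the last four being "112 days, 140 days, 168 days, 196 days after the last treatment administration date in extension". The section provides N/A for percentiles that are not reached. It has no such rule for time points.

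The section also says: "Only data from the follow-up extension period will be included". SAP 5.2.1 fixes that period: "The extension follow-up period will be defined as the Month 12 date or (treatment discontinuation date+1) up to the extension follow-up end date".

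On the protocol side, section 10.2.2 states: "Up to Month 6 Extension FU visit, the subject will continue to record on her eDiary". At that visit the diary is collected and deactivated (10.2.2.3). Section 10.2 places the visit at "Month 6 Extension FU (Day 505) for the Follow-up Period", with a window of 7 days either way. Early stoppers attend 168 days, plus or minus 7, after their last intake. Section 10.2.1 puts a completer's last dose on the day before the Month 12 visit.

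**The concern.** There are two separate problems in one section.

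The first is that a survival estimate needs women under observation at the time it refers to. If diary recording ends well before 196 days, a probability and interval printed in that row describe some earlier time. A reader of the table could not tell whether the figure was observed, carried forward, or resting on a handful of late visits.

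The second is that the event definition and the clock both start at the last dose, while the data start at the follow-up period. For completers that start is tied to the Month 12 visit and not to the last dose. Where the two are more than a day apart, bleeding in between is off-drug, meets the event definition, and is not counted. Any resulting error can only lengthen the time to menses.

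**Working it through.** **Inputs**
- Month 12: Day 337, window 3 days either way, so Day 334 to 340 (Protocol 10.2).
- Last dose of a completer: the day before, so Day 333 to 339, nominally Day 336 (Protocol 10.2.1).
- Month 6 follow-up visit: Day 505, window 7 days either way, so Day 498 to 512 (Protocol 10.2).
- Early stoppers: 161 to 175 days after last intake (Protocol 10.2.2.3).
- SAP clock: end date minus last-dose date plus 1 (SAP 6.6.8.5).

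**The schedule reproduces.** Month 12 is 1 + 28 × 12 = Day 337. Adding 28, 84 and 168 gives Days 365, 421 and 505, as stated.

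**Longest observable time on the SAP clock**
- Completers, nominal: 505 − 336 + 1 = 170.
- Completers, longest: 512 − 333 + 1 = 180.
- Completers, shortest: 498 − 339 + 1 = 160.
- Early stoppers: 168 + 1 = 169, range 161 + 1 = 162 to 175 + 1 = 176.

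The 196-day point is 196 − 180 = 16 days past the maximum. With a last dose on Day 336, the diary would have to run to Day 336 + 196 − 1 = 531, which is 19 days after the latest allowed visit.

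**Variants.** SAP Table 2 counts the Month 6 follow-up visit as 168 days from the actual Month 12 date. That gives 170 nominally, 177 with 7 days' tolerance and 184 with 14. Protocol 11.2 has dosing through Month 12 inclusive, whereas 10.2.1 has no intake at that visit. The two passages must be reconciled, but a dose on the Month 12 date would only shorten the range, to 498 − 340 + 1 = 159 through 512 − 334 + 1 = 179.

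**The 168-day point.** There are 7 × 15 = 105 allowed pairs of Month 12 and follow-up dates, and 70 of them (67%) give at least 168 days. For early stoppers it is 9 of 15 allowed days (60%). These count calendar dates with equal weight and are not shares of women. They show only that censoring falls close to the last usable time point, so the number at risk there matters.

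**The gap between last dose and follow-up data**
- Completer dosed as planned: last dose on the Month 12 date minus 1, data from the Month 12 date. Days lost: 0, for every Month 12 date in the window.
- Early stopper: data from the discontinuation date plus 1. Days lost: 0, if the discontinuation date is the last-dose date.
- Completer whose last dose is k days before the planned one: days lost = k.

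The third case is possible within the documents. SAP 5.5 accepts a Month 12 PK sample up to 2 days after the last intake, which corresponds to k = 1. A linzagolix kit covers 30 days (Protocol 11.3). Dispensed on Day 306 (Month 11 at its earliest), it lasts to Day 335, which is 4 days short of Day 339 if Month 12 falls on Day 340 and no tablets are left over. Of the 49 in-window date pairs, 10 give some shortfall. The add-back kit does not run short (98 days from Day 250 reach Day 347), so the recorded last-dose date might not move even then.

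**The case against.** The best defence of the 196-day row is that the SAP works with actual dates, not theoretical ones. The documents acknowledge remote visits during the pandemic, disruption at Ukrainian sites and off-schedule Month 12 visits, so a few women may be observed that long. This stands: the claim that nobody could ever be at risk at 196 days is stronger than the documents allow. It does not rescue the row, because an estimate resting on a few deviating visits needs at least a number at risk beside it.

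It can also be said that 196 is simply the next step of a 28-day grid and sweeps up events after day 168. That is a fair account of how it arose. Such a figure would nevertheless be the estimate at the last event, labelled with a later day.

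The analysis is descriptive, with no hypothesis tests, and the full curve and a by-subject listing are already planned. This stands too and limits the importance of the point.

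On the gap, the defence is largely right. On the plan's own rules no days are lost. A reader might infer that first menses are generally dated late, or late by about one cycle. The documents support neither. A delay of that size would need a whole bleeding episode to begin and end inside the gap; bleeding that continues to the Month 12 date is late only by days within the gap. Nor does the per-protocol rule on Month 12 visits more than 14 days off schedule help that reading: it compares the visit with its planned date, not with the last dose.

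**Conclusion.** The first part holds on protocol dates. Diary time on the SAP clock cannot exceed 180 days for completers or 176 for early stoppers, and 196 lies 16 days beyond the larger figure. Unless every woman in a group has already had menses, the 196-day value would be undefined, carried forward, or drawn from out-of-window visits only. This rests on the protocol's windows and on diary recording ending at the Month 6 follow-up visit.

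The second part holds only conditionally. The data restriction conflicts with the section's own event definition for any completer whose last dose is earlier than the day before Month 12. Her first menses can then be dated too late, never too early. How often this happens and by how much is not given in the documents.

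Severity is minor: one row of a descriptive safety table, and a wording conflict that has no effect when dosing runs as planned.

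**What to change.** In SAP 6.6.8.5:

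1. Delete the 196-day time point, make 168 days the last tabulated estimate, and print the number at risk at every time point. Events on days 169 to 180 then fall outside the table but still appear on the curve and in the by-subject listing.
2. Replace the restriction to follow-up-period data with a statement that all eDiary bleeding records from the day after the last extension dose up to the Month 6 follow-up visit are used. This matches the section's event definition and clock, and changes nothing for women dosed up to the day before Month 12.

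The cost is SAP wording, a small programming change, and the loss of one reported time point.

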6.7. Unblinding of subjects

Subjects that were unblinded during the course of the study will be summarized and listed. The cumulative unblinding history report from IWRS will be provided by the Sponsor in an excel format. This file will only contain unblinding status but no treatment information.

6.8. **Exploratory Analyses**

Bone turnover markers will be analyzed on the Extension Safety Analysis Set.

Blood samples for exploratory bone biomarkers include, but may not be limited to, collagen type 1 β -carboxy-telopeptide (CTx), procollagen 1 Intact N-Terminal (P1NP), bone-specific alkaline phosphatase (B-ALP) and osteocalcin as part of clinical chemistry, and are collected at Month 6, Month 9 and Month 12 and Month 3 Extension Follow-up. These exploratory data will be kept blinded up to the unblinding of the database.

CRS-BS-TP-000005 V 2.0

Actual values and changes from baseline will be summarized overtime by treatment group. Bone marker data will be reported in listings as well.

7. CHANGES TO PLANNED ANALYSES

The Follow-up Extension Analysis Set, defined in protocol as:

All subjects from the main study who completed the 6 months of treatment in the extension study and who entered the Post-Treatment Follow-Up Period. Subjects will be analyzed according to randomized treatment.

Is changed to:

All subjects from the main study who entered the extension study and received at least one dose of study drug with the exception of subjects whose Month 6 assessment subsequently met any of the discontinuation criteria, and who entered the Post-Treatment Follow-Up Period. Subjects will be analyzed according to randomized treatment.

The rationale for this modification is that subjects that entered the Follow-up period, even if they did not complete the 6 months of extension treatment should be followed up for efficacy.

SAP Version	Update description	SAP Section	Reason
V2.0	Assessments from Local Laboratories (due to Covid-19 situation) will be excluded from summary tables of laboratory data	Section 6.6.3	Local laboratories may not have comparable normal ranges, thus it does not make sense to pool them with central laboratory data in numeric summaries.
V2.0	Biopsy assessments from Local Laboratories (due to war situation in Ukraine) should be flagged in listings. Information is available in Data Management Closed Queries File.	Section 6.6.8.1	Due to war situation in Ukraine, there were some Biopsies assessed locally. This information should be incorporated in listings.
V2.0	Addition of listings for PAP Smear for both abnormality and diagnosis information.	Section 6.6.8.3	PAP Smear listings were missing from original SAP Version.
V3.0	All protocol deviations related to a particular subject will be presented in the data listings.	Section 4.2	There were PD records which had missing subject ID and thus were not

Updates from SAP Amendments since SAP V1.0 are summarized in the table below:

CRS-BS-TP-000005 V 2.0

Page **75** of **99**

Kissei / Cytel Confidential: This is a controlled document and shall not be changed, saved, copied or reproduced by any unauthorized person.

			related to any particular subject. These records were excluded in the listings.
V3.0	Added additional condition when imputing missing date for AE onset: The missing Day & Month will be replaced by "01 JAN.", unless other information provides evidence that the event should not be defined as treatment- emergent AE.	Section 6.2.6.2	When imputing the missing Day & Month for AE onset date, other information (time course and onset timing for events) may help provide evidence to define treatment-emergent AE.
V3.0	Assessments from the main study (i.e before Month 6) will be also displayed in the safety and efficacy tables and listings.	Section 6.4. Section 6.6	To provide more efficacy/safety information.
V3.0	The summary tables for HRPQ, HRUQ, PGIC, mPGIS will be summarized up to Month 6 Extension FU and not up to Month 12.	Section 6.4.3.26, Section 6.4.3.27, Section 6.4.3.31, Section 6.4.3.32	To provide more efficacy information.
V3.0	Added by-subject listings for HRPQ, PROMIS, EQ-5D-5L for follow-up extension analysis set.	Section 6.4.3.26, Section 6.4.3.29, Section 6.4.3.30	To provide more efficacy information.
V3.0	For AEs and post-treatment AEs, summary tables and tables by SOC and PT are presented for selected periods/population, not all periods/populations.	Section 6.6.1	Only TAEAs summary tables and tables by SOC and PT will be presented for all periods/populations.
V3.0	Not all measurements of Bone Mineral Density (BMD) by Dual-Energy X-ray Absorptiometry (DXA) will be presented. Only those	Section 6.6.2	Only acceptable measurement will be presented.

CRS-BS-TP-000005 V 2.0

Page **76** of **99**

	measurements with an acceptable DXA measurement will be listed.		
V3.0	Added the summary table and listing for Follicle-Stimulating Hormone (FSH) at local laboratory for subjects that do not resume menses at M3 ExFU visit.	Section 6.6.3	Added as part of safety analyses.

8. **REFERENCES**

Not applicable

9. APPENDICES

Г

9.1. Appendix A: Analgesic change during treatment period

Use of No Analgesics at Baseline				
Analgesic used during Screening	Analgesic dose status at end of study	Assessment of Change		
	None**	Stable/Decrease		
None	Narcotic analgesic and/or ibuprofen is started	Increase		
Use of Only Ibuprofen at Ba	seline			
Analgesic uses at Baseline	Analgesic dose status at end of study	Assessment of Change		
	Dose stopped, decreases, or is stable**	Stable/Decrease		
ibuprofen	Dose increases by 15% or more	Increase		
	Narcotic analgesic is substituted or added	Increase		
Use of Only Narcotic Analgesic at Baseline				
Analgesic uses at Baseline	Analgesic dose status at end of study	Assessment of Change		
	Dose stopped, decreases, or is stable**	Stable/Decrease		
Narcotic analgesic	Dose stopped and ibuprofen substituted (any dose)	Stable/Decrease		
	Dose decreases and ibuprofen added (any dose)	Stable/Decrease		

CRS-BS-TP-000005 V 2.0

Page **79** of **99**

Kissei / Cytel Confidential: This is a controlled document and shall not be changed, saved, copied or reproduced by any unauthorized person.

	Dose stable and ibuprofen added (any dose)**	Increase
	Dose increases by 15% or more	Increase
Use of Ibuprofen and Narco	tic Analgesic at Baseline	
Analgesic uses at Baseline	Analgesic dose status at end of study	Assessment of Change
	lbuprofen dose stops + narcotic analgesic use stops, decreases, or is stable**	Stable/Decrease
	Ibuprofen use stops + narcotic analgesic dose increases by more than 15%	Increase
	Ibuprofen dose decreases + narcotic analgesic use stops, decreases, or is stable**	Stable/Decrease
ibuprofen + narcotic analgesic	Ibuprofen dose decreases + narcotic analgesic dose increases by more than 15%	Increase
	lbuprofen dose stable + narcotic analgesic use	Stable/Decrease
	stops, decreases, or is stable**	
	Ibuprofen dose stable + narcotic analgesic dose	Increase
	increases by more than 15%	

Ibuprofen dose increases by more than 15% + narcotic analgesic use stops	Stable/Decrease
lbuprofen dose increases by more than 15% + narcotic analgesic dose decreases	Stable/Decrease
lbuprofen dose increases by more than 15% + narcotic analgesic dose is stable**	Increase
Ibuprofen dose increases by more than 15% + narcotic analgesic dose increases by 15% or more	Increase

**Stable =Dose is the same as the screening dose or increases by less than or equal to 15% of the screening dose. In addition, a subject can increase the monthly total dose of analgesics by one pill of analgesic (either ibuprofen or narcotic) and still be considered stable.

9.2. Appendix B: EHP-30 Scoring

The mapping of the response categories for the EHP-30 core questionnaire and the modular questionnaire is as follows:

0 = Never, 1 = Rarely, 2 = Sometimes, 3 = Often, 4 = Always

For the modular questionnaire, records indicating "Not Applicable" will be excluded from summary/analysis.

Missing data will not be imputed.

The EHP-30 core questionnaire is structured into the following five dimensions.

- 1. Pain (Questions 1 11)
- 2. Control and Powerlessness (Questions 12 17)
- 3. Emotional Well-Being (Questions 18 23)
- 4. Social Support (Questions 24 27)
- 5. Self-Image (Questions 28 30)

Each dimension for the core and modular questionnaire is calculated on a scale from 0 to 100.

0 = best possible health status as measured by the questionnaire; 100 = worst possible

CRS-BS-TP-000005 V 2.0

Page 81 of 99

health status as measured by the questionnaire. Within each dimension, assessment will be based on the following equation:

Sum of scores for each dimension / 4 (maximum score per item) * number of items in the dimension

Sum of the scores for each item in the dimension Core questionnaire: Pain $((Ql + Q2 + Q3 + Q4 + Q5 + Q6 + Q7 + Q8 + Q9 + Q10 + Q11)/44) \times 100$ 2. Core questionnaire: Control and Powerlessness $((Q12 + Q13 + Q14 + Q15 + Q16 + Q17)/24) \times 100$ 3. Core questionnaire: Emotional well-being $((Q18 + Q19 + Q20 + Q21 + Q22 + Q23)/24) \times 100$ 4. Core questionnaire: Social Support $((Q24 + Q25 + Q26 + Q27)/16) \times 100$ 5. Core questionnaire: Self-Image $((Q28 + Q29 + Q30)/12) \times 100$ Modular questionnaire: Sexual intercourse $((C1 + C2 + C3 + C4 + C5)/(total or 20)) \times 100$ For Modular questionnaire: Sexual intercourse, if a "not applicable" box is physical for one or more of the five items (Questions C1 - C5) the sector is

checked for one or more of the five items (Questions C1 - C5), the score is calculated by omitting those "not applicable" items from the numerator and the denominator.

If any of the components of a dimension on the core or modular questionnaire is missing, no score will be calculated for that dimension. For example, if answer for Q1 is missing, no score for Core questionnaire: Pain is calculated. If answer for C1 is missing, no score for Modular questionnaire: Sexual intercourse will be calculated.

